1.0 Objectives

1.1 Study Objectives

The specific aims of the current study are to:

1) Examine the longitudinal effect of very low nicotine content (VLNC) cigarettes on changes in task-related functional neural activation within brain circuitry associated with incentive salience valuation and executive function. We hypothesize that, for the VLNC group compared to the normal nicotine content (NNC) group:

- a. Reactivity to smoking vs. pleasant odors within incentive salience circuitry will decrease.
- b. Reactivity to monetary rewards within incentive salience circuitry will increase.
- c. Activity during decision-making and inhibitory control within executive control circuitry will increase.

2) Assess the longitudinal effect of VLNC cigarettes on changes in effective (directional) connectivity between incentive salience and executive control brain circuitry. We hypothesize that, for the VLNC group compared to the NNC group:

- a. The influence of executive control over incentive salience circuitry, measured during task demands that simultaneously engage both processes, will increase.
- b. The influence of non-smoking reward salience circuitry over smoking salience circuitry during the odor cue reactivity task will increase.

3) Establish measurable and objective neural outcomes of successful reductions in smoking dependence.

1. We hypothesize that changes in functional activation and effective connectivity over the course of the VLNC intervention will be correlated with reductions in subjective and behavioral assessments of smoking dependence, including the number of cigarettes smoked per day, subjective reports of dependence, craving, and withdrawal.

4) Assess the effect of VLN Cigarettes vs NNC cigarettes on the levels of salivary miRNAs targeting dopamine, glutamate, acetylcholine and GABA-related transcripts over 6-weeks.

1. We hypothesize that the VLNC group will have significantly more changes in miRNA expression than the NNC group. A two-way repeated measures ANOVA will be conducted to compare changes in miRNA expression over three time points for the VLNC and NNC groups.

5) Determine if within-subject changes in miRNA expression are associated with changes in fMRI BOLD signal during smoking cue-reactivity and inhibitory control tasks for the VLNC group over 6-weeks.

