8.3 Statistical methods

Data Analysis. Images will be preprocessed using FSL, including registration to high resolution anatomical images and standard space, brain extraction, slice timing correction, spatial and temporal smoothing, intensity normalization, physiological noise correction, and motion correction for 6 motion parameters and artifacts identified via ICA-AROMA.⁶³ For task-based images, contrasts of the relevant conditions will be determined during first level analyses as described above and averaged across multiple runs for each participant.

Aim 1: Examine the longitudinal effect of VLNC cigarettes on changes in task-related functional neural activation within brain circuitry associated with incentive salience valuation and executive function.

Treatment-related within-subject and between-subject changes in BOLD activation during all fMRI tasks will be assessed in linear mixed-effects models using FSL software. Whole-brain analyses and ROI analyses based on pre-determined salience and executive control circuitry will be conducted. Paired t-tests will identify anatomical regions showing statistically significant differences from baseline to 6-week scans across groups.

Aim 2: Assess the longitudinal effect of VLNC cigarettes on changes in effective (directional) connectivity between incentive salience and executive control brain circuitry. Dynamic causal modeling (DCM) using SPM12 software will measure effective connectivity between ROIs in the incentive salience and executive control networks.⁶⁴ Specifically, DCM identifies models with task-specific increases in the dependence of the BOLD activity timecourses between a priori selected nodes and estimates directionality. We expect that the use of the VLNC cigarettes will strengthen the influence of the executive control over incentive salience circuitry during the smoking Go/NoGo and temporal discounting tasks. ROIs will be selected a priori for these analyses. Given the novelty of the odor cue reactivity task, active brain circuitry identified in Aim 1 will be included as nodes in the DCM model to test the hypothesis that non-smoking reward circuitry will exert an increasing influence over smoking salience circuitry. Connectivity estimates from the models will be included in a mixed-effects ANOVA to determine between-subjects and within-subject effects across the trial.

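### Odor-task DCM nodes are drawn from Aim 1 results in the same scans with no selecting contrast named; if that contrast is change, the matching connectivity-change test is not independent of selection

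*Combined protocol and SAP*

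**What the plan says.** All the relevant text on method is in section 8.3.

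- **Aim 1, model:** "Treatment-related within-subject and between-subject changes in BOLD activation during all fMRI tasks will be assessed in linear mixed-effects models using FSL software".
- **Aim 1, scope:** "Whole-brain analyses and ROI analyses based on pre-determined salience and executive control circuitry will be conducted".
- **Aim 1, identification of regions:** "Paired t-tests will identify anatomical regions showing statistically significant differences from baseline to 6-week scans across groups".
- **Aim 2, general description of DCM:** the method is said to find "increases in the dependence of the BOLD activity timecourses between a priori selected nodes and estimates directionality".
- **Aim 2, Go/NoGo and temporal discounting:** "ROIs will be selected a priori for these analyses".
- **Aim 2, odor task:** because the task is new, "active brain circuitry identified in Aim 1 will be included as nodes in the DCM model".
- **Aim 2, test:** "Connectivity estimates from the models will be included in a mixed-effects ANOVA to determine between-subjects and within-subject effects across the trial".

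Hypothesis 2b in section 1.1, stated for VLNC compared with NNC, is that "The influence of non-smoking reward salience circuitry over smoking salience circuitry during the odor cue reactivity task will increase". Section 2.3 plans two scans per participant, at baseline and at 6 weeks. No contrast, threshold, hold-out sample or independence condition is given for choosing the odor-task nodes.

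**The concern.** The odor-task nodes are chosen from, and their connectivity tested in, one dataset: the same people and the same two scans. That is harmless when the selecting statistic is unrelated to the tested one under the null. It is not harmless when both measure change from baseline to week 6, because chance change in activation then picks the nodes, and any related chance change in coupling carries over into the test.

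A literal reader of Aim 1 finds only analyses of change from which to select: the mixed models of treatment-related change and the paired t-test. An analyst could also settle the contrast after seeing the maps. At stake is the error rate of the odor-task connectivity result. The within-subject part matters because section 8.2 justifies the 2:1 allocation by power for within-subject analyses. The general description of DCM in the same paragraph, with nodes fixed a priori, does not fit the odor-task rule.

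**Working it through.** **Plan figures.** The plan states no error rate for the DCM tests, so there is none to reproduce. Section 8.2 uses a type I error of .05, taken here as nominal. Its sample sizes (28, 86, 28 at f = 0.25 and 80% power) do reproduce with three measurements and a within-person correlation of 0.5, both assumed, but nothing below depends on them.

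**Inputs.** From the plan: 50 VLNC and 25 NNC (7.1), two scans (2.3), alpha .05 (8.2). Assumed: the null correlation ρ between a participant's change in activation (a) and change in coupling (c), shown at 0, 0.3, 0.5 and 0.7; equal variances in the arms; no true change. The sketch uses one region's activation change per connection, which simplifies a DCM.

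**1. Selection on pooled change, test of time.** The pooled mean changes in a and c correlate at ρ, so Z_c = ρ·Z_a + √(1 − ρ²)·E, with E independent noise. The error rate is P(|Z_c| > 1.96, given selection on |Z_a|).

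| Selection rule | ρ = 0 | 0.3 | 0.5 | 0.7 |
|---|---|---|---|---|
| Largest of 20 candidate regions (simulated) | 5% | 8–9% | 16–17% | 27–28% |
| Region significant at p < .05 (bivariate normal) | 5% | 10% | 19% | 33% |
| Region significant at p < .001 (bivariate normal) | 5% | 18% | 42% | 76% |

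The two ends in the first row come from a simulation with 50 and 25 participants and from the normal approximation. With 10 to 50 candidates at ρ = 0.5 the error is 13–21%.

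**2. Selection on pooled change, test of arm by time.** With unit variances, the covariance between pooled mean activation change and the arm difference in coupling change is

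(1/75)·(50·ρ/50 − 25·ρ/25) = (ρ − ρ)/75 = 0.

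Selection therefore carries no information about the arm contrast. Simulated error at 50:25 is 0.048 to 0.058 over the whole range of ρ. With an SD ratio of 1.5 between arms the cancellation fails: 0.111 at ρ = 0.5. The pooled-variance test is already at 0.085 without any selection, so most of that excess is a separate matter.

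**3. Selection on the arm-by-time map, test of arm by time.** The covariance of the two arm differences is ρ·(1/50 + 1/25), and each has variance (1/50 + 1/25), so the correlation is again ρ. Simulated error at ρ = 0.3, 0.5 and 0.7 is about 10%, 17% and 28% (largest of 20), or 10%, 18% and 32% (p < .05). The time test then stays near 5%.

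**4. Selection on activation averaged over both scans and both arms.** Cov(a₀ + a₆, a₆ − a₀) = Var(a₆) − Var(a₀) = 0 when the two scans have equal variance. Simulated error is 0.050 to 0.055 for time and 0.047 to 0.052 for arm by time.

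**5. Selection on MRI Visit 1 alone.** With an assumed test-retest correlation of 0.5 and unit variances, Cov(a₀, a₆ − a₀) = 0.5 − 1 = −0.5 and Var(a₆ − a₀) = 2·(1 − 0.5) = 1. The selecting statistic therefore correlates −0.5·ρ with coupling change. Simulated time-test error is about 6–8% (largest of 20) or 7–11% (p < .05); arm by time stays near 5%.

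**The case against.** The best defence is that the plan says active circuitry, not circuitry that changed. The reason it gives, novelty, explains not knowing which regions the odors activate and gives no reason to select on six-week change. Hypothesis 2b needs two kinds of node, smoking-salience and non-smoking reward; a contrast between odors separates these, and a baseline-to-week-6 t-test does not. Aim 1 also lists whole-brain and pre-determined ROI analyses built on first-level condition contrasts. This stands as far as it goes: a reader might infer that the plan definitely selects on change, and the text does not say so. But it does not name a task-activation contrast either.

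A reader might also infer that hypothesis 2b will draw excess false-positive support. Under the pooled paired t-test quoted above it does not, because 2b is an arm contrast and step 2 shows it is unaffected with equal variances. Inflation of 2b needs selection on the arm-by-time map, which the text neither states nor rules out.

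It is likewise tempting to say that the primary endpoint is compromised because it rests on the same task. Section 1.2 names reactivity to tobacco odor and smoking dependence; DCM connectivity is neither.

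Finally, activation and coupling are different quantities, and the size depends wholly on ρ. That is fair. Zero is possible, but it cannot be presumed when both are estimated from the same BOLD time courses. The rates are also two-sided: in the hypothesised direction alone, largest-of-20 selection gives 4.6%, 8.2% and 14.2% against 2.5%.

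**Conclusion.** The point holds as a conditional one. The odor-task nodes come from the data in which they are tested, the selecting contrast is unstated, and the Aim 1 analyses that are described would, followed literally, select on change.

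- **Selection on pooled change:** the within-subject test runs at about 8–28% for ρ of 0.3 to 0.7 with largest-of-20 selection, higher with a strict significance threshold, and 5% at ρ = 0. The 2b contrast stays near 5%.
- **Selection on arm by time:** the 2b contrast itself runs at about 10–30%.

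These sizes assume ρ, equal arm variances and a one-region simplification; none is given in the documents. The reach is one of three DCM tasks within one aim, in a study that section 8.2 also describes as pilot data. It is worth correcting because the correction is small.

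**What to change.** In section 8.3, Aim 2, state that odor-task nodes are chosen with a named task contrast and threshold (odor against neutral), averaged over both scans and pooled over arms, within the pre-determined salience masks. Alternatively, use a priori ROIs, as for the other two tasks. Fix the rule before any change map or arm-level map is examined, and align the general DCM sentence with it. Selecting on MRI Visit 1 alone is second best, since it leaves a slight bias in the time test.

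The cost is about one sentence and no new data. The small downside is that a region that changed but is not task-active on average may not become a node.

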We currently know little about how neural activity and connectivity of the incentive salience and executive control circuitry change during recovery. Given the advancements in pharmacotherapy and non-invasive brain stimulation techniques,^{30,31} gaining a nuanced understanding of how brain circuitry adapts during rehabilitation could identify neural targets for treatment. VLNC cigarettes have been used as an extinction-based cessation treatment to reduce the rewarding effects of cigarettes by significantly reducing nicotine delivery during smoking.^{6,34} Over the course of a VLNC extinction trial with nicotine replacement therapy, smokers' reactivity in the amygdala to smoking over neutral visual cues decreased.³⁴ Participants who successfully abstained in a quit attempt following the extinction trial had reduced cue reactivity in the thalamus and ventral striatum compared to participants who relapsed.³⁴

The central hypothesis underlying this award is that brain circuitry associated with incentive salience valuation and executive control can be altered by treatment interventions and, consequently, serve as potential biomarkers of dependence reduction and cessation treatment outcomes. In a double-blind, randomized controlled trial, dependent smokers will be randomized to a 6-week VLNC cigarette intervention (N=50) or a 6-week normal nicotine content cigarette control condition (NNC; N=25). Participants will undergo fMRI scans at baseline, and 6-weeks to investigate the treatment-related modulation of brain circuitry involved in incentive salience valuation and executive control. Imaging tasks will assess the incentive salience of smoking cues and non-smoking rewards and executive function to identify changes in functional activity within, and effective connectivity between, known salience and executive control brain circuitry. A novel fMRI task using specialized odor presentation equipment and fMRI sequences will assess neural cue reactivity to smoke odors.

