7.0 Study Design and Procedures

7.1 Study Design

This is a two-arm, randomized, double-blind parallel group trial. Smokers will be randomly assigned to smoke very low nicotine content (VLNC) (n=50) or normal nicotine content (NNC) (n=25) SPECTRUM cigarettes for 6 weeks. Participants and study staff will be blind to the experimental cigarette allocation until the study is complete. The groups will be stratified by gender.

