8.2 Sample size determination

Dependent smokers of low SES (n=75) will be recruited for the current study through the TCORS study call center (protocol #2213). Two-thirds of the sample (n=50) will be randomized to the VLNC group to maximize power for the within-subjects repeated measures analyses while still allowing for an analysis of between-subjects effects. There is not currently an accepted method for determining sample size a priori for repeated measures fMRI designs. With repeated measures behavioral data, to detect a medium effect size ($f=0.25$) with 80% power and a Type I error rate of .05, a sample size of 28 is required to detect within-subjects effects, 86 for between-subject effects, and 28 for within x between interactions. The estimate for detecting such effects with fMRI is likely somewhat higher; however, my mentors have found within-subject effects with similar tasks that will be used for this project with comparable sample sizes; smoking cue reactivity (n=22)⁶¹ card-guessing task (n=44)⁵, and the n-back task (n=33)⁶². Thus, we estimate that the current design will have adequate power to detect small to medium within-subjects effects and medium to large between-subjects effects. The design will serve as pilot data to determine sample size for future studies. TCORS found retention rates of 85% for their 18-week trial and a prior 6-week VLNC intervention found retention rates at 92%.⁴⁹ Retention for the proposed study will likely be higher given frequent contact with participants (3-week visit and two phone-check-ins); however, with a conservative estimate of 80% retention and adequate compliance, the final sample size (n=60) would still be adequately powered. We will recruit until we have 75 study completers. It is likely that participants that complete informed consent at the remote screening will be ineligible. Therefore, we expect around 90 participants to complete informed consent and 75 to complete the entire study.

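### Aim 2 does not name the arm-by-time contrast that tests its hypothesis, and comparing arms at week 6 adjusted for the pre-exposure baseline scan would test it more precisely

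*Combined protocol and SAP*

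**What the plan says.** Section 1.1 states Aim 2 as changes in directional connectivity, hypothesised to increase in the VLNC group relative to the NNC group. Section 2.3 sets the imaging schedule: "Participants will undergo fMRI scans at baseline, and 6-weeks". Section 7.2.2 has study cigarettes handed out at the end of MRI Visit 1, so the baseline scan precedes exposure.

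The Aim 2 analysis in section 8.3 is: "Connectivity estimates from the models will be included in a mixed-effects ANOVA to determine between-subjects and within-subject effects across the trial". For Aim 1 the same section says: "Treatment-related within-subject and between-subject changes in BOLD activation during all fMRI tasks will be assessed in linear mixed-effects models using FSL software", and adds paired t-tests of baseline against week 6 across groups. No baseline covariate is mentioned for either aim, and the mean structure of the Aim 1 models is not given.

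Section 8.2 takes a medium effect (f = 0.25) "with 80% power and a Type I error rate of .05" and states that "a sample size of 28 is required to detect within-subjects effects, 86 for between-subject effects, and 28 for within x between interactions". Section 7.1 allocates participants to "very low nicotine content (VLNC) (n=50) or normal nicotine content (NNC) (n=25) SPECTRUM cigarettes for 6 weeks". No baseline to week-6 correlation is given.

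**The concern.** In a two-occasion mixed ANOVA the between-subjects effect is the arm difference averaged over both scans. Treatment cannot have affected the baseline scan, so this average carries half of any week-6 effect. The within-subject effect is time averaged over arms and does not compare VLNC with NNC. Only the arm-by-time term matches the hypothesis, and the analysis text does not name it.

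Even with that term named, precision is lost. With two scans it is a two-sample t-test on week 6 minus baseline. A baseline measured before exposure in a randomised trial can instead be used as a covariate, which targets the same treatment effect with less residual variance whenever r is below 1. With 25 participants in the control arm, that precision is worth having.

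Two things are at stake: clarity about which result answers Aim 2, and the power of that result.

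**Working it through.** **Inputs from the documents.** Alpha 0.05, 80% power, f = 0.25 and 28/86/28 (section 8.2); 50 versus 25 (section 7.1); two scans (section 2.3).

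**Assumptions.** Outcome SD 1 at both scans; r from 0.2 to 0.9; a true week-6 arm difference of 0.5 SD. All results are for one two-sided test at 0.05, with no correction for multiple connections or voxels.

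**Step 1: reproduce the plan's figures.** For two groups, m measurements and total N, the noncentrality is f²Nm/(1−r) for the within and interaction tests and f²Nm/(1+(m−1)r) for the between test.
- With m = 3 and r = 0.5: 0.0625×28×3/0.5 = 10.5 and 0.0625×86×3/2 = 8.06. These reach 80% power, giving 28/86/28 exactly.
- With m = 2, the number of scans, the same inputs give 34/98/34.

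So r = 0.5 is the correlation implied by the plan's own figures. Those figures are offered for behavioural data, so the three measurements are not in themselves an error.

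**Step 2: what each term estimates.** Let δ be the week-6 arm difference. Randomisation makes the expected baseline difference zero.
- Arm main effect: (0+δ)/2 = δ/2.
- Time main effect: average change over arms, no arm comparison.
- Arm-by-time: δ − 0 = δ.
- Week 6 adjusted for baseline: δ.

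**Step 3: residual variances.**
- Change score: 2(1−r).
- Baseline-adjusted: 1−r², times (N−3)/(N−4) for estimating the slope.
- Two-scan mean: (1+r)/2.

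Apart from the small slope term, adjusted over change is (1−r²)/[2(1−r)] = (1+r)/2.

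**Step 4: power at 50 versus 25.** √(1/50+1/25) = 0.2449. At r = 0.5:
- Arm-by-time: 0.5/(0.2449×1) = 2.041 on 73 df, power 0.52.
- Adjusted: 0.5/(0.2449×√(0.75×72/71)) = 2.341 on 72 df, power 0.64.
- Arm main effect: 0.25/(0.2449×√0.75) = 1.179 on 73 df, power 0.21.

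| r | Variance ratio | Power, arm-by-time | Power, adjusted | Gain (points) |
|---|---|---|---|---|
| 0.2 | 0.60 | 0.36 | 0.53 | 17.6 |
| 0.3 | 0.65 | 0.40 | 0.55 | 15.6 |
| 0.5 | 0.75 | 0.52 | 0.64 | 11.5 |
| 0.7 | 0.85 | 0.74 | 0.80 | 6.1 |
| 0.8 | 0.90 | 0.89 | 0.92 | 2.5 |
| 0.9 | 0.95 | 0.995 | 0.996 | 0.1 |

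The difference detectable with 80% power falls from 0.82 to 0.67 SD at r = 0.3, from 0.70 to 0.61 at r = 0.5 and from 0.44 to 0.42 at r = 0.8. At 40 versus 20, the plan's 80% retention case, it falls from 0.78 to 0.68 at r = 0.5.

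**Step 5: the plan's own effect.** In a balanced two-by-two layout f = 0.25 is a difference in change of 4×0.25 = 1.0 SD. At r = 0.5 and 50 versus 25, power goes from 0.98 to 0.996.

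**Check by simulation.** With 20,000 simulated trials at 0.5 SD and r = 0.5, power was 0.516 (arm-by-time), 0.633 (adjusted) and 0.213 (arm main effect). Under no effect the rejection rates were 0.051, 0.050 and 0.049.

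**The case against.** A reader might infer that the investigators mean to report the arm main effect over both scans as the treatment effect, with power near 21%. The documents do not support that. Section 1.1 frames Aim 2 as a between-arm difference in change, section 8.2 sizes the interaction explicitly, and a mixed ANOVA with arm and time ordinarily contains it. What stands is narrower: section 8.3 does not name it as the test. The relevant power comparison is arm-by-time against baseline-adjusted.

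A reader might also infer that adjustment brings clearly more power whatever the data look like, and at no cost. The gain depends on r and the true effect, neither of which the documents give. It nearly vanishes at r = 0.9 and is 1.5 points at the plan's own f with r = 0.5. The cost is small, not nil.

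Nor is having baseline among the outcomes a fault in itself. A mixed model with baseline means constrained equal across arms is essentially as efficient as covariate adjustment. An ordinary mixed ANOVA does not impose that constraint. For Aim 1 the mean structure is unstated, so a loss there cannot be shown, only guarded against.

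Finally, the arm-by-time test is valid and unbiased under randomisation. Chance baseline imbalance feeding into change scores is another view of the same variance loss, not a separate harm. Connectivity is not among the primary endpoints in section 1.2, and section 8.2 describes the design as pilot data for later studies. This limits the stakes but does not argue against a better-specified test.

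**Conclusion.** The point holds as a gap in specification and a missed gain in precision, not as an invalid analysis. The two effects named for Aim 2 do not test its hypothesis, and the one that does is not named. Naming arm-by-time would close the gap. Adjusting for baseline would also cut the variance of the contrast by a factor of about (1+r)/2, or 0.75 at the r = 0.5 implied by the plan's own sample sizes.

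For an assumed 0.5 SD difference at 50 versus 25, the gain is about 11 to 18 points of power for r between 0.2 and 0.5, about 6 at r = 0.7, and 2.5 or less from r = 0.8. These sizes rest on equal SDs at both scans, a linear baseline relation, complete data on 75 participants and a single test without multiplicity correction. The change is worth making before analysis.

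**What to change.** In section 8.3, for each connectivity parameter (Aim 2) and each ROI mean (Aim 1), make the treatment test the VLNC−NNC difference at week 6, adjusted for the participant's own baseline value and the gender stratum, two-sided, with its 95% CI. A mixed model with baseline means constrained equal across arms is an acceptable equivalent. In whole-brain maps, enter the baseline map as a voxelwise covariate. State that the arm main effect averaged over both scans will not be reported as a treatment effect.

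The cost is SAP wording and a little code, one or two degrees of freedom per model, an assumed linear baseline slope, and a stated rule for participants without a usable baseline scan. No additional data are needed.

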1.2 Primary Study Endpoints

Changes in neural reactivity to tobacco odor and changes in smoking dependence.

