- Prior to the visit, an unblinded member of the study team will randomize the participant to either the VLNC or NNC cigarette group based on a pre-determined block randomization list. The unblinded study member will identify the cigarette packs with the assigned nicotine content by NRC code and prepare them for redistribution by re-labeling each pack with the participant ID number and a label indicating these are research cigarettes. The unblinded study member will keep records of the RTI log numbers of the packs dispensed to each participant at each visit. At the end of MRI Visit 1 participants will be given an ample 6-week supply of their assigned cigarette (125% of baseline cigarettes per day) and instructed to only smoke study cigarettes until their next scheduled appointment. Participants may contact the study team to receive more study cigarettes if they run out prior to their next visit unless this is more than a 100% increase from their baseline CPD. Participants will be instructed to continue completing the daily REDCap cigarette log surveys that they receive via text message and will also be given paper cigarette logs to track use throughout the day.

Time commitment: 2 hours

7.2.3 Remote visit 1 (scheduled for +1 to +3 day(s) of in person MRI visit)

Participants will complete the following procedures over Zoom

1. REDCap Survey Questionnaire

- a. Depression (CESD)
- b. COPD (CCQ)
- c. Psychological Distress (Kessler K6)
- d. Nicotine Dependence
- e. Anxiety (ASQ)
- f. Sleep Disturbance
- g. Cigarette Liking
- h. Stages of Change
- i. Perceived Stress

2. Interview

- a. Concomitant medications
- b. Adverse event trigger questions

3. Out of scanner tasks

- a. Participants will complete a monetary temporal discounting task. During this computerized task, participants will choose between two options with specified dollar amounts and time delays to receipt of money (see MRI task image below).
- b. Participants will complete a computerized stroop interference task where they will view color words printed in the same color (i.e., blue, red, yellow, green), color words printed in an incongruent color (e.g., “blue” printed in red), and color neutral words printed in color (e.g., “hat” printed in red). Participants will be asked choose what color each word is printed in by pressing a button labeled to indicate each color.

7.2.4 Phone call 1

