7.2.7 Text message with quit attempt survey (Week 18 ± 5 days)

Participants will receive a text message with a REDCap survey link inquiring about current smoking status and past 12-week quit attempts. Participants will be sent a second text message if they do not complete the survey within 72 hours of the first message. The study coordinator will call participants who are unwilling or unable to receive text messages to complete the survey.

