Aim 3: Establish measurable and objective neural outcomes of successful reductions in smoking dependence. FSL's Randomise one-sample t-test will be conducted on change scores to determine if changes in BOLD activity are associated with reductions in subjective markers of dependence (FTND, HONC, MNWS, QSU), cigarettes smoked per day, and quit intention and success. Changes in connectivity estimates will be correlated with changes in subjective and behavioral outcomes.

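### Aim 3's BOLD analysis is a one-sample t-test on change scores, which tests the mean change and not its association with reduced dependence

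*Combined protocol and SAP*

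**What the plan says.** The Aim 3 hypothesis in section 1.1 is about correlation: "We hypothesize that changes in functional activation and effective connectivity over the course of the VLNC intervention will be correlated with reductions". The reductions meant are those in subjective and behavioural measures of dependence. It covers both activation and connectivity.

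Section 8.3 gives the Aim 3 analysis in two sentences. The one for activation begins "FSL's Randomise one-sample t-test will be conducted on change scores to determine if changes in BOLD activity are associated with reductions in subjective markers". It then names its targets in full: "of dependence (FTND, HONC, MNWS, QSU), cigarettes smoked per day, and quit intention and success". That makes seven measures: four questionnaires, cigarettes per day, quit intention and quit success. The other sentence specifies a correlation of change with change, but only for connectivity estimates.

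For Aim 1, the same section says: "Paired t-tests will identify anatomical regions showing statistically significant differences from baseline to 6-week scans across groups".

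No other section gives a model for the Aim 3 activation analysis. The plan does not say whether Aim 3 uses both arms or the VLNC arm only.

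**The concern.** The named test and its stated purpose do not match. A one-sample t-test on BOLD change scores has the null hypothesis that the mean change is zero. The dependence measures are named as the target of the inference but have no role as covariate, regressor or contrast. The test therefore gives one map per task contrast, and that map would serve unchanged for all seven measures.

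Followed literally, the analysis can mislead in two ways. A mean BOLD shift from any cause, such as treatment or habituation to a second scan, would be reported as an association with reduced dependence. A real association without a mean shift would be missed. Section 2.3 rests the study's central hypothesis on brain circuitry as a potential biomarker of reduced dependence, and this is the activation analysis that bears on that idea.

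**Working it through.** The documents give no effect size, power or sample size for Aim 3, so there is no figure of the plan's own to reproduce. The core point is algebraic. The sizes below are illustrations with assumed effects.

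**Inputs.** Section 8.2 gives 75 planned completers, a lower final sample of 60, a VLNC arm of 50 and a Type I error rate of 0.05. Two-sided testing, normal change scores, mean shifts of 0.2 to 0.4 SD and correlations of 0.2 to 0.4 are assumptions.

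**Step 1: what each test uses.** Let d be a participant's BOLD change and x the change in a dependence measure.

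- One-sample test: t = mean(d) / (SD(d)/√N). x does not appear.
- Slope test: t = r√(N−2) / √(1−r²), where r is the sample correlation of d and x.

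For one simulated set of 75 BOLD changes, the one-sample t is 2.92 whether the paired dependence change correlates with it at −0.93, −0.03, 0.22 or 0.90.

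**Step 2: relation to Aim 1.** A paired t-test on two scans is a one-sample t-test on their difference. On the simulated data both give t = 2.9241. The parametric p is 0.0046 and the sign-flip p is 0.0043. Restricted to 50 participants, t becomes 2.2850. So Aim 3 repeats Aim 1's statistic if participants and contrasts are the same, and differs from it if Aim 3 is VLNC only.

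**Step 3: mean shift, no association.** Power of the one-sample test comes from the noncentral t with noncentrality δ√N, where δ is the shift in SD units. For δ = 0.3 and N = 75, noncentrality is 0.3 × 8.66 = 2.60 and power is 72.7%.

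| Mean shift (SD) | N=75 | N=60 | n=50 |
|---|---|---|---|
| 0.2 | 40% | 33% | 28% |
| 0.3 | 73% | 63% | 55% |
| 0.4 | 93% | 86% | 79% |

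At N = 75 the slope test rejects about 5% in each row (simulation), which is its nominal level.

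**Step 4: true correlation, no mean shift.** The one-sample test rejects about 5% at every sample size. Slope-test rejection rates (20,000 simulated trials per setting) are:

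| True r | N=75 | N=60 | n=50 |
|---|---|---|---|
| 0.2 | 41% | 33% | 29% |
| 0.3 | 75% | 65% | 57% |
| 0.4 | 95% | 90% | 83% |

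Check by Fisher z at r = 0.3, N = 75: atanh(0.3) × √72 = 0.3095 × 8.485 = 2.63; 2.63 − 1.96 = 0.67; power about 75%.

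**Step 5: what the correct test could detect.** The smallest correlation with 80% power is tanh[(1.960 + 0.842)/√(N−3)]. For N = 75 that is tanh(2.802/8.485) = 0.32; for 60 it is 0.36 and for 50 it is 0.39. These are for one test. With Bonferroni correction over seven measures (0.05/7 = 0.00714), power at r = 0.3 falls to 47%, 36% and 28% for 75, 60 and 50. The rates in Step 4 are therefore not the power this study would have.

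**Step 6: does image-wise correction remove the mismatch?** A rough simulation at N = 75 used 200 smoothed positions, 40 of them carrying the effect, with familywise 5% control by maximum |t|. A shift of 0.3 SD without association gave a significant position in 81% of one-sample runs and 6% of slope runs. A correlation of 0.3 without a shift gave 5% and 84%. Monte Carlo error is up to 2.5 points. The layout is invented, so only the pattern matters: correction does not remove the mismatch.

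**The case against.** The best reply is that this is incomplete wording and not a wrong analysis. The sentence itself gives association as the purpose, and section 1.1 speaks of correlation. A one-group Randomise design can carry a demeaned covariate whose slope is tested. An analyst who reads the sentence for its purpose would add one, and the harm would disappear.

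That reading is possible, but the plan does not state it. It names a specific test, and that test does not involve the dependence data. Adding a covariate while keeping the contrast on the mean would still test the mean, so the contrast has to be written down as well.

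Several limits on the point do stand:

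- It affects only the activation half of Aim 3. Connectivity is already to be correlated, and Aims 1 and 2 have their own models.
- Section 1.2 lists "Changes in neural reactivity to tobacco odor and changes in smoking dependence" as primary endpoints. The association between the two is not itself one.
- Section 8.2 describes the design as a source of pilot data.
- The overlap with Aim 1 is conditional. Section 1.1 frames Aim 3 around the VLNC intervention, which hints at that arm alone, whereas Aim 1's paired tests run across groups.

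These limit the reach of the error. They do not make the named test answer its question.

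**Conclusion.** The Aim 3 activation analysis is wrong as written. The stated test has a null hypothesis about the mean, its result does not depend on any of the seven measures, and nothing elsewhere in the plan supplies the missing model. That conclusion needs no assumption about effect size.

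The rejection rates do rest on assumed effects and on a single uncorrected test. With 75 participants and moderate effects (0.3 SD or r = 0.3), the named test would respond to an irrelevant mean shift about 73% of the time and would find a real association only at its 5% error rate. The sentence should be corrected before the data are analysed.

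**What to change.** Replace the one-sample t-test with a Randomise general linear model: BOLD change regressed on the demeaned baseline-to-week-6 change in a measure, one model per measure, with the intercept as a nuisance term and the regressor's contrast tested by permutation. The same text should settle the following.

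- **Quit success.** The week 18 text survey is the one "inquiring about current smoking status and past 12-week quit attempts", so there is no baseline-to-week-6 change to use. Enter the outcome itself as the regressor.
- **Instruments.** The visit schedules list a nicotine dependence questionnaire without naming FTND or HONC. They also do not say which form measures quit intention; Stages of Change and the quit choice survey are candidates. Identify each one.
- **Baselines.** MNWS and QSU are listed at MRI visit 1. The nicotine dependence questionnaire is listed in section 7.2.3 at "Remote visit 1 (scheduled for +1 to +3 day(s) of in person MRI visit", which is after study cigarettes are handed out. Name the visit that supplies each baseline.
- **Participants.** State both arms or VLNC only. If pooled, say whether the reported association includes the treatment effect or is adjusted for arm.
- **Multiplicity.** Seven measures give seven maps per task contrast. Say whether they are corrected jointly.

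The cost is a revised paragraph and design matrix, and one or two degrees of freedom. No new data, visits or participants are needed.
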